7.2 Safety Assessments

7.2.1 Medical History

Medical history, including clinically significant past and present medical conditions, will be recorded at screening visit. Lung cancer history will be recorded separately at that time. Signs and symptoms of the patient's cancer diagnosis and/or comorbidities present prior to the first dose of study treatment should be noted and recorded separately. Interval history of symptoms should be collected at each visit. Any worsening or newly identified signs or symptoms after C1D1 will be recorded in the AE log.

7.2.2 Physical Exam and Vital Signs

Exam and vital signs should be performed as per Section 6.6. Clinically significant findings noted during screening and prior to first dose of study treatment will be documented separately, while those noted after C1D1 will be collected in the AE log.

7.2.3 Laboratory Safety Assessments

Safety labs will be collected for each cycle prior to pembrolizumab infusion and sitravatinib release. Labs to be collected are summarized in *Table 7*.

Table 7: Laboratory Safety Parameters

Hematology Panel	Blood Chemistry Panel
Hemoglobin/Hematocrit	Aspartate aminotransferase
Platelet count	Alanine aminotransferase
White blood cell count	Alkaline phosphatase
Neutrophil count	Total bilirubin (if Total bilirubin is $\geq 2 \times$ ULN and no evidence of Gilbert's syndrome, then fractionate into direct and indirect bilirubin)
Lymphocyte count	
Urinalysis	Sodium
Blood	Potassium
Protein	Chloride
	Bicarbonate or carbon dioxide (CO ₂)
Thyroid Function Test	Blood urea nitrogen (BUN) or urea
Thyroid-stimulating hormone with reflex free T4	Creatinine
	Albumin
	Total Calcium

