1.3.5 Clinical Experience with Sitravatinib

1.3.5.1 Sitravatinib Clinical Safety Experience

Sitravatinib has been administered to cancer patients in multiple clinical studies, including Phase 1 and 2 studies as a single-agent and in combination with other anticancer therapies in non-squamous non-small cell lung cancer (NSCLC), urothelial cancer (UC), renal cell carcinoma (RCC), and hepatocellular carcinoma (HCC), among other malignancies. In addition, sitravatinib in combination with nivolumab is being evaluated in a Phase 3 study in non-squamous NSCLC.

As of 26 Jun 2021, safety data are available for a total of 1106 subjects with advanced solid malignancies treated with sitravatinib, either as a single agent (n = 220), in combination with the PD-1 inhibitor nivolumab (n = 565), combination with ipilimumab/nivolumab (n=10), combination with pembrolizumab/EV (n=13) or in combination with tislelizumab (n = 300).

Among the 1106 subjects with solid malignancies who were treated with sitravatinib, 1012 (92%) experienced at least one sitravatinib-related AE. Among the 1106 subjects, sitravatinib-related Grade 3 events were reported in 485 subjects (44%) overall.

Sitravatinib-related Grade 3 events reported in $\geq 5\%$ of subjects were hypertension (16%), diarrhea (7%), and fatigue (5%). Sitravatinib-related Grade 4 AEs were reported in 26 subjects (2%). The only Grade 4 sitravatinib-related events occurring in more than 1 subject by Preferred Term was lipase increased in 5 subjects (0.5%). Sitravatinib-related Grade 5 AEs were reported in 12 subjects, including death in 6 subjects, cardiac arrest in 2 subjects, and cardiac failure, hepatic encephalopathy, ischemic stroke, and respiratory failure in 1 subject each.

For full details and most up to date information regarding safety data please see the most current version of the Investigator's Brochure.

1.3.5.2 *Sitravatinib Clinical Efficacy in NSCLC Patients*

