5.2.3 Pembrolizumab Dose Modification or Discontinuation

Interruption or discontinuation of pembrolizumab may be required for some toxicities as summarized in *Table 2*. Treatment of suspected pembrolizumab related adverse events is discussed in Section 5.3.3. Dose reductions of pembrolizumab are not allowed. Dosing interruptions are permitted in the case of medical / surgical events or logistical reasons not

related to study therapy (e.g., elective surgery, unrelated medical events, patient vacation, and/or holidays). Subjects should be placed back on study therapy within 3 weeks of the scheduled interruption, unless otherwise discussed with the Sponsor Investigator. The reason for interruption should be documented in the patient's study record.

Table 2: Dose Modification Guidelines for Drug-Related Adverse Events for Pembrolizumab

Toxicity	Hold Treatment For Grade	Timing for Restarting Treatment	Discontinue Subject
Diarrhea/Colitis	2-3	Toxicity resolves to Grade 0-1.	Toxicity does not resolve within 12 weeks of last dose or inability to reduce corticosteroid to 10 mg or less of prednisone or equivalent per day within 12 weeks.
	4	Permanently discontinue	Permanently discontinue
AST, ALT, or Increased Bilirubin	2	Toxicity resolves to Grade 0-1	Toxicity does not resolve within 12 weeks of last dose.
	3-4	Permanently discontinue (see exception below) ¹	Permanently discontinue
Type 1 diabetes mellitus (if new onset) or Hyperglycemia	T1DM or 3-4	Hold pembrolizumab for new onset Type 1 diabetes mellitus or Grade 3-4 hyperglycemia associated with evidence of beta cell failure.	Resume pembrolizumab when patients are clinically and metabolically stable.
Hypophysitis	2	Toxicity resolves to Grade 0-1	Toxicity does not resolve within 12 weeks of last dose or inability to reduce corticosteroid to 10 mg or less of prednisone or equivalent per day within 12 weeks.
	3-4	Withhold until clinically stable or permanently discontinue depending on severity	Permanently discontinue depending on severity.
Hyperthyroidism	3-4	Withhold until clinically stable or permanently discontinue depending on severity	Toxicity does not resolve within 12 weeks of last dose or inability to reduce corticosteroid to 10 mg or less of prednisone or equivalent per day within 12 weeks.

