5.3.1.2 General Management of Sitravatinib Related Hematological Toxicities

Hematological toxicities are not a frequent cause of treatment interruption or discontinuation of sitravatinib treatment. Observed \geq Grade 3 hematological events that are considered to be causally related to sitravatinib should initially be managed using treatment interruption until resolution of toxicity to \leq Grade 2. In addition, dose reduction of sitravatinib will be implemented in the following cases:

- Grade 3 or 4 febrile neutropenia;
- Grade 4 neutropenia persisting for \geq 8 days; or
- Grade 4 thrombocytopenia of any duration or Grade 3 thrombocytopenia with bleeding.

Table 3: Dose Modifications for Sitravatinib Toxicity

Toxicity	Grade	Treatment Delay	Dose Modification
General non-hematologic toxicity ¹	1	Not required	None
	2	Not required	Asymptomatic: None required
			Symptomatic: None required. Early dose reduction to the next lower dose level is recommended over treatment interruption.
	3-4	Hold until \leq grade 1 or return to baseline	Resume at reduced dose. Exceptions presented in footnotes ²
Hematologic toxicities	1-2	Not required	None
	3	Hold until \leq grade 2	Reduce dose for grade 3 febrile neutropenia or grade 3 thrombocytopenia with bleeding
	4	Hold until \leq grade 2	Reduce for grade 4 febrile neutropenia, grade 4 neutropenia lasting \geq 8 days or grade 4 thrombocytopenia
Hypertension	1-2	Not required	None required
	3	Not clinically significant ³ : Not required	Decrease dose if unresponsive to anti-hypertensive treatment
		Clinically significant ³ : Hold until \leq grade 2 or return to baseline	Resume at decreased dose level
	4	Discontinue	Discontinue
Transaminitis	1	Not required	None required
	2	Not required	Decrease by one dose level
	3-4	Hold until \leq grade 1 or return to baseline	If resolution occurs within 29 days, decrease by 1 dose level. If no resolution within 29 days, discontinue sitravatinib

¹ Management of selected sitravatinib toxicities as per Section 5.3.2

² Patients may resume at the same dose in the following cases:

- a. Grade 3 or 4 electrolyte abnormality that is not clinically complicated and resolves spontaneously or with conventional medical treatment within 72 hours;

b. Grade 3 amylase or lipase elevation that is not associated with symptoms or other clinical (e.g., electrolyte abnormalities, radiographic changes) manifestations of pancreatitis.

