Increased amylase and lipase have been observed in subjects treated with sitravatinib and have been reported with other inhibitors of the VEGF pathway. Most sitravatinib-related treatment-emergent events of increased amylase and lipase were asymptomatic while some were associated with signs and/or symptoms of pancreatitis. Treatment with sitravatinib may continue without dose modification (eg, interruption or reduction) in cases of asymptomatic

amylase and/or lipase increases in the absence of other clinical evidence of pancreatitis (eg, symptoms, electrolyte abnormalities, radiographic changes) at the Treating Investigator's discretion. Sitravatinib should be interrupted for any grade pancreatitis and the subject managed according to standard-of-care. After resolution of pancreatitis, sitravatinib resumption is at the discretion of the Treating Investigator; if pancreatitis is assessed as sitravatinib treatment-related and treatment is resumed, a dose reduction is recommended.

Immune-Related Adverse Events (irAEs)

Single agent sitravatinib has not been associated with irAEs. However, the potential exists for irAEs associated with sitravatinib to contribute to irAEs associated with pembrolizumab treatment. In the event of a Grade 2 irAE during study treatment, administration of sitravatinib and pembrolizumab will be interrupted until the event stabilizes to Grade ≤ 1 (see Section 5.3.3 on pembrolizumab associated adverse event treatment). At the time of resumption of sitravatinib dosing, a dose reduction may be implemented at the discretion of the Treating Investigator.

Management of Grade 3 and 4 irAEs should be performed as in section on pembrolizumab related adverse events management (Section 5.3.3). Recurrent Grade 3, or any Grade 4, irAEs should generally be managed with permanent discontinuation of pembrolizumab, and temporary or permanent interruption of sitravatinib. Sitravatinib may be resumed at the same or lower dose at the discretion of the Treating Investigator once the event stabilizes to Grade ≤ 1 .

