5.3.3.2 Management of Selected Pembrolizumab-Related Adverse Events

Pneumonitis:

For Grade 2 events pembrolizumab should be held and treatment with corticosteroids initiated. When symptoms improve to Grade 1 or less, steroid taper should be started and continued over no less than 4 weeks. For Grade 3-4 events, immediately treat with intravenous steroids. Administer additional anti-inflammatory measures, as needed. Add prophylactic antibiotics for opportunistic infections in the case of prolonged steroid administration.

Diarrhea/Colitis:

Subjects should be carefully monitored for signs and symptoms of enterocolitis (such as diarrhea, abdominal pain, blood or mucus in stool, with or without fever) and of bowel perforation (such as peritoneal signs and ileus). All subjects who experience diarrhea/colitis should be advised to drink liberal quantities of clear fluids. If sufficient oral fluid intake is not feasible, fluid and electrolytes should be substituted via IV infusion. GI consultation should be considered for Grade 2 or higher diarrhea/colitis. For Grade 2 diarrhea/colitis that persists greater than 3 days despite supportive treatment and anti-diarrheals, pembrolizumab should be held and oral steroids should be administered. For Grade 3 or 4 diarrhea/colitis, pembrolizumab should be held and IV or oral corticosteroids should be administered. For grade 3-4 diarrhea that persists > 4 days despite oral steroids, treat with intravenous steroids followed by high dose oral steroids. If not improving despite IV steroid administration, may also consider additional anti-inflammatory treatments. When symptoms improve to Grade 1 or less, steroid taper should be started and continued over no less than 4 weeks.

New Onset Type 1 diabetes mellitus (including diabetic ketoacidosis [DKA]) or \geq Grade 3 Hyperglycemia, if associated with ketosis (ketonuria) or metabolic acidosis (DKA):

For T1DM or Grade 3-4 Hyperglycemia associated with metabolic acidosis or ketonuria, initiation of insulin is recommended. Pembrolizumab may be held while glucose control is

obtained. Evaluate patients with serum glucose and a metabolic panel, urine ketones, glycosylated hemoglobin, and C-peptide.

Hypophysitis:

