6.6.1 Laboratory Testing

Details regarding specific laboratory procedures/assessments to be performed in this trial are provided in Section 7.2.3 and in the Study Calendars (Section 6.1).

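### Amylase and lipase have no scheduled test although sitravatinib dosing rules depend on them; glucose is covered only implicitly by an un-itemised CMP

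*Combined protocol and SAP*

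**What the plan says.** **Which labs are collected.** Section 7.2.3 states: "Safety labs will be collected for each cycle prior to pembrolizumab infusion and sitravatinib release". It then refers to Table 7 ("Labs to be collected are summarized in" that table). The chemistry column covers liver enzymes, bilirubin, electrolytes, renal function, albumin and calcium. Glucose, amylase and lipase are not in it.

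Section 6.6.1 gives a second source: the laboratory procedures "to be performed in this trial are provided in Section 7.2.3 and in the Study Calendars". Both calendars (6.1.1 and 6.1.2) require a CBC and a CMP at screening, at every cycle, at the Day 8 safety visit and at End of Treatment. They also schedule urinalysis and TSH. Neither has a row for amylase or lipase, and the contents of the CMP are not listed.

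**Rules that use these values.**
- Table 3 footnote 2b (Section 5.3.1.2) allows sitravatinib to resume at the same dose after a "Grade 3 amylase or lipase elevation that is not associated with symptoms" or other signs of pancreatitis.
- Section 5.3.2 notes: "Increased amylase and lipase have been observed in subjects treated with sitravatinib". It adds that most such events were asymptomatic, and it lets dosing continue unmodified in those cases at the Treating Investigator's discretion.
- Table 2 (Section 5.2.3) says: "Hold pembrolizumab for new onset Type 1 diabetes mellitus or Grade 3-4 hyperglycemia associated with evidence of beta cell failure". For such cases Section 5.3.3.2 says: "Evaluate patients with serum glucose and a metabolic panel, urine ketones, glycosylated hemoglobin, and C-peptide".

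**Prior experience.** Section 1.3.5.1 pools 1106 subjects treated with sitravatinib alone or in combinations. Increased lipase, in 5 subjects (0.5%), is the only related Grade 4 term reported in more than one.

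**The concern.** A rule graded on a laboratory value works only if the value is obtained. If most amylase and lipase elevations are silent, testing prompted by symptoms will miss most of them. Three things follow:

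- The text on asymptomatic elevations applies only to patients who happen to be tested.
- No pre-treatment value is required against which a later one can be judged.
- The reported rates depend on each site's testing habits. Adverse events are a secondary endpoint (Section 4.4.2), and Section 4.4.4.1 says the combination has not been evaluated first-line, so a low rate could be misread as reassurance.

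**Working it through.** **1. Is there a scheduled test?** These are the laboratory- or echocardiogram-defined harms that Section 5.3.2 discusses, set against the schedule:

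| Harm in 5.3.2 | Scheduled measurement | Where |
|---|---|---|
| Thyroid dysfunction | TSH at screening, cycle 3, every other cycle, End of Treatment | Calendars, Table 7 |
| Decreased LVEF | ECHO at screening, cycle 3, End of Treatment | Calendars, 7.2.5 |
| Proteinuria | Urinalysis at screening, through treatment, End of Treatment | Calendars, Table 7 |
| Increased transaminases | AST and ALT each cycle | Table 7 |
| Increased amylase or lipase | None | – |

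Amylase/lipase is the only one without a scheduled test.

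**2. Is there a baseline?** For Grade 3-4 non-hematologic toxicity, Table 3 holds sitravatinib until Grade 1 or less, or until the value is back at baseline. No amylase or lipase value is required at screening, so the second limb cannot be applied reliably to them.

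**3. Reproduce the stated rate.** 5/1106 = 0.452%, which rounds to the stated 0.5%. The treatment subgroups listed in 1.3.5.1 add to 220 + 565 + 10 + 13 + 300 = 1108, not 1106; with either denominator the rate rounds to 0.5%.

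Exact (Clopper–Pearson) 95% limits:
- lower = Beta quantile(0.025; 5, 1102) = 0.147%
- upper = Beta quantile(0.975; 6, 1101) = 1.052%

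**4. Scale it to this trial.** Take n = 70 (Section 4.5.1) and assume that the pooled rate p carries over. Expected events = n × p, and the chance of at least one = 1 − (1 − p)^n.

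| Rate p | Expected in 70 | Chance of at least one |
|---|---|---|
| 0.147% | 0.10 | 10% |
| 0.452% | 0.32 | 27% |
| 1.052% | 0.74 | 52% |

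For Grade 3, which footnote 2b concerns, only a bound is available. Section 1.3.5.1 lists the related Grade 3 events seen in at least 5% of subjects, and neither amylase nor lipase is among them. Each was therefore below 5%, that is, fewer than 0.05 × 70 = 3.5 expected here on the same assumption.

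**5. Direction of the error.** Incomplete testing can only miss elevations, so the observed rates are biased low. The amount cannot be computed: the documents give no overall amylase or lipase rate, and no asymptomatic fraction beyond saying it is the majority.

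**6. Glucose.** Table 7 omits it, but the calendars schedule a CMP throughout. If that panel includes glucose, as is conventional (an assumption), then glucose is measured at screening and at every cycle. What is left is a mismatch between an itemised table and an un-itemised calendar entry.

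**The case against.** Several points on the other side are sound.

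- **Glucose.** A reader might infer from Table 7 alone that glucose is never measured, or never captured. The documents do not support this. Section 6.6.1 makes the calendars a source of required labs, the CMP is scheduled throughout, and no case report form is available to show what is recorded. The Table 2 hold also needs evidence of beta-cell failure, and Section 5.3.3.2 has a written work-up.
- **Detection by chance.** A reader might infer that amylase and lipase elevations would surface only by luck. That goes too far, since suspected pancreatitis would prompt testing. What is lost is systematic detection of silent changes.
- **Frequency.** Increased lipase accounts for 5 of the 26 subjects with related Grade 4 events, and a reader might infer that it is common. The rate among treated subjects is 0.5%, and it comes from earlier pooled use, not from this trial.
- **Design preference.** Section 5.3.2 lets dosing continue through asymptomatic elevations, so testing on symptoms is a tenable clinical choice. If it is the choice, the safety analysis should say so.
- **Recording rule.** Section 8.1.1 records an abnormal result as an adverse event only under listed conditions, so some silent elevations could stay out of the adverse event data even if tested. This is true but does not defeat the point. Elevations that change dosing or lead to further testing are still recorded, and Section 10.4 puts laboratory data in the database. Silent elevations would then have to be summarised from laboratory values.

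**Conclusion.** The point holds for amylase and lipase. No scheduled test exists in Table 7 or either calendar, dosing text depends on the values, and the protocol itself says most elevations are silent. Reported rates will therefore be under-ascertained, with no required baseline. For glucose, the finding is limited to a wording mismatch.

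The size is modest: about 0.3 Grade 4 lipase events expected in 70 patients (0.10 to 0.74 over the exact interval), if the pooled rate applies to this population and combination. The primary endpoint, sample size, type I error and power are unaffected. The change is worth making because it is cheap and adverse events are a secondary endpoint.

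**What to change.** 1. Reconcile Table 7 and both Study Calendars with Tables 2 and 3 and Section 5.3.2, so that the values these rules grade on have a baseline and an on-treatment measurement. Amylase and lipase could come from the chemistry sample already drawn, assuming site laboratories can add them. The cost is a low-cost assay and somewhat more asymptomatic findings to review.
2. If the sponsor prefers not to schedule them, add one sentence to Section 9.3: amylase and lipase were not systematically tested, and their adverse event rates are not incidence estimates.
3. Name glucose in Table 7, or itemise the CMP, so that the two agree. If the CMP already includes glucose, this needs no new sample.

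The testing schedule and any dose rule are for the sponsor to decide. The request is only that the sections agree, or that the limitation be stated.

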7.2.4 Electrocardiograms

Triplet 12 lead EKGs to be performed as outlined in the Study Calendars (Section 6.1) for baseline/screening, and on C1D8 and C2D1 for the main study group (Group A) and C2D8 and C3D1 for the pembrolizumab run-in group (Group B). Thereafter EKGs will be performed as clinically indicated.

7.2.5 Echocardiogram

Echocardiogram will be performed at baseline/screening, within 7 days prior to C3D1, and at end of treatment. ECHO can be performed thereafter as clinically indicated at the Treating Investigator's discretion if there are signs or symptoms of cardiotoxicity.

8 Adverse Event Reporting

8.1 Evaluating Adverse Events

8.1.1 Definitions

An Adverse Event (AE) is any reaction, side effect or other undesirable medical event that occurs during participation in a clinical trial, regardless of treatment group or suspected causal relationship to study treatment. An AE can therefore be any unfavorable and unintended sign (including an abnormal laboratory finding, for example), symptom, or disease temporally associated with the use of a medicinal product or protocol-specified procedure, whether or not considered related to the medicinal product or protocol-specified procedure. Any worsening (i.e., any clinically significant adverse change in frequency and/or intensity) of a preexisting condition that is temporally associated with the use of study drugs, is also an adverse event. Adverse events may also occur in screened subjects during any pre-allocation baseline period as a result of a protocol-specified intervention, including washout or discontinuation of usual therapy, diet, placebo treatment or a procedure.

An abnormal laboratory test result should be recorded as an AE in the CRF only if it is associated with one or more of the following: clinical symptoms; additional testing, treatment or intervention; change in study dosing; discontinuation from study treatment; or if it is considered by the Sponsor or Treating Investigator to be an AE.

Progression of the cancer under study is not considered an adverse event unless it is considered to be drug related by the Treating Investigator.

Assessment of AEs will include type, incidence, severity (graded by the National Cancer Institute [NCI] Common Terminology Criteria for Adverse Events [CTCAE, Version 5.0]), timing, seriousness, and relatedness to study treatment.

8.1.2 Recording AEs

All observed or volunteered AEs will be recorded in source documents and reported in the CRF along with severity, relatedness and expectedness as defined below (Sections 8.1.3, 8.1.4, 8.1.5). The best available medical terminology should be used to describe AEs in

source documents and CRFs. Terms describing the diagnosis are preferred over individual signs and symptoms of the diagnosis. If determination of the diagnosis is delayed, record signs and symptoms and add the diagnosis as an additional AE when available; follow all recorded AEs to resolution. The actual date of onset should be recorded in all cases.

Ongoing AEs that change in attribution or severity should have the date of change entered as the “end date” and a new AE record should be opened with the changed details.

